 - 11.1 Direct Medical Costs
 - 11.2 Direct Non-Medical Costs
 - 11.3 Indirect (Patient Time) Costs
 - 11.4 Short-term Cost Analysis
 - 11.5 Long-term Cost-Effectiveness Analysis
 - 11.6 Sustainability of the Intervention
- 12. Efficacy Parameters
 - 12.1 Primary Efficacy Parameter
 - 12.2 Secondary Efficacy Parameter
 - 12.3 Exploratory Efficacy Parameters
- 13. Safety Monitoring and Adverse Events
 - 13.1 Adverse Events (AE) and Serious Adverse Events (SAE)
 - 13.2 Data Safety Monitoring Board (DSMB)
 - 13.3 Stopping Rules
- 14. Statistical Considerations
 - 14.1 Statistical Methods
 - 14.2 Sample Size Justification
 - 14.3 Data Management
- 15. Privacy protection
- 16. Organizational Structure

Abbreviations:

ADHF- acute decompensated heart failure

SPPB- short physical performance battery

6MWD- 6-minute walk distance

KCCQ- Kansas City Cardiomyopathy Questionnaire

SF-12- 12-item short form health survey

HF- heart failure

QOL- quality of life

PND- paroxysmal nocturnal dyspnea

BNP- B-type natriuretic peptide

ADL- activity of daily living

RPE- rate of perceived exertion

EQ-5D-5L- Euroqol 5-dimension 5-level

GDS- Geriatric Depression Scale

MoCA- Montreal Cognitive Assessment

DSMB- data safety monitoring board

AE- adverse event

SAE- serious adverse event

REDCap- research electronic data capture

LOT-R – Life Orientation Test

1. Overview of the REHAB-HF Study

REHAB-HF: A Trial of Rehabilitation Therapy in Older Acute Heart Failure Patients, is a multicenter, randomized, attention-controlled, single-blind trial designed to examine the hypothesis that, in addition to standard care, a novel, tailored, progressive, multi-domain rehabilitation intervention administered to older patients with acute decompensated heart failure (ADHF) beginning early during hospitalization and continuing for 12 weeks will improve physical function and key clinical outcomes, including the rate of rehospitalization.

There will be 3 lead centers, Wake Forest Baptist Health, Duke University Medical Center, and Thomas Jefferson University and Hospital. Each lead center may recruit up to 3 geographically-close, tightly-affiliated 'satellite' sites under their direct management and budgetary control. Together, these sites will recruit a total of 360 consenting patients ≥ 60 years old hospitalized with ADHF. Following informed consent and baseline testing, the participants will be randomized in a 1:1 fashion to receive a 12-week novel, progressive, multi-domain rehabilitation and exercise training intervention or attention control. The multi-domain rehabilitation intervention will include endurance, mobility, strength, and balance training and will be tailored based on participant performance in each of these domains. It will begin upon randomization during the hospitalization and will continue 3 times per week in an outpatient setting. Participants randomized to the attention control arm will receive all services ordered by their primary physician and will be contacted bi-weekly by study staff. All participants will undergo measures of physical function and quality of life at baseline, 1 month, and 3 months. Clinical events will be monitored for 6 months following the index hospitalization.

By testing a novel rehabilitation intervention supported by multiple levels of evidence, this trial will address a critical evidence gap in the care of older patients with ADHF. The REHAB-HF results have the potential to shift paradigms by improving physical function and quality of life as well as clinical outcomes. If successful, the results could have a major impact on the management of patients with ADHF, the most common Medicare discharge diagnosis.

2. Study Objectives

2.1 Primary Objective

To conduct a multicenter, randomized, attention-controlled, single-blind trial of a novel, tailored, progressive, multi-domain, 12-week physical function intervention in 360 older patients with ADHF in order to test the following primary specific hypothesis: The REHAB-HF intervention will improve physical function, as measured by the short physical performance battery (SPPB).

2.2 Secondary Objective

To systematically collect clinical outcomes data during the 6 months following the index hospitalization to test the following secondary hypothesis: The REHAB-HF intervention will reduce the 6-month all-cause rehospitalization rate.

2.3 Other Objectives

- 1. To assess the economic impact of the intervention by comparing medical costs between treatment arms, inclusive of the cost for rehabilitation therapy, relative to its associated changes in health outcomes.
- 2. To estimate the proportion of the reduction in rehospitalizations explained by the intervention's effect on the SPPB score.
- 3. To examine the effect of the intervention on these exploratory endpoints:

- 1. Change in the Kansas City Cardiomyopathy Questionnaire (KCCQ) total score and physical component score at 3 months
- 2. Change in 6-minute walk distance (6MWD) at 3 months
- 3. Change in component scores of the SPPB at 3 months
- 4. Change in the 12-item short form health survey (SF-12), depression, and cognition measures at 3 months
- 5. Change in frailty status at 3 months
- 6. All-cause rehospitalizations at 1 month and 3 months
- 7. All-cause rehospitalizations 6 months from the date of randomization
- 8. All-cause combined rehospitalization and death at 6 months
- 9. Global rank endpoint of SPPB score + all-cause rehospitalization + death
- 10. Heart failure (HF)-specific rehospitalizations
- 11. Cardiovascular events
- 12. All-cause rehospitalization days
- 13. Total hospitalization days post-randomization
- 14. Total facility-free days alive
- 15. Deaths
- 16. Falls
- 17. Change in biomarkers at 3 months
- 18. Blood-based bioenergetics profiling.

3. Background

ADHF is the leading cause of hospitalization in persons > 60 years in the United States. Hospitalized ADHF is associated with severely reduced health-related quality of life (QOL), persistently high rehospitalization rates,(1) markedly increased mortality, and costs over \$39 billion per year.(2) Current HF management guidelines, even when perfectly adhered to, have had only modest impact on ADHF outcomes, particularly rehospitalizations in the older population.(1;3-5) Furthermore, several recent trials of new interventions to improve ADHF outcomes, such as telemonitoring,(6;7) alternative diuretic regimens,(8-11) novel agents(11;12) and biomarker guidance have been negative.(9;13) This suggests outcomes in older ADHF patients may be driven partly by mechanisms that are not addressed by current approaches.

Multiple lines of emerging evidence suggest that severely reduced physical function and frailty strongly contribute to adverse outcomes in older patients with hospitalized ADHF (14) We and others have shown that even when stable with compensated cardiovascular function, older patients with chronic HF have particularly severe impairments in physical function (14-16) due to the combined effects of aging, cardiovascular dysfunction, and impaired skeletal muscle function.(17-27) As patients with chronic HF transition to ADHF, physical function worsens markedly both because of HF decompensation and accelerated physical deconditioning.(19;28;29) This is further exacerbated by the hospital processes, including forced bed rest which can markedly accelerate physical dysfunction.(30-36) We and others have shown that after resolution of the acute HF symptoms and congestion, older ADHF patients continue to have marked impairments in physical function, including strength, balance, mobility and endurance, and that most patients meet formal definitions of frailty.(28;29;37-39) Furthermore, these deficits persist and some patients never recover baseline function.(14;33;40-43) This occurs during the most vulnerable, high risk period for rehospitalization and adverse outcomes - up to 6 months post discharge. (44;45) We hypothesize that this physical frailty predisposes patients to adverse outcomes and that this cascade of events contributes to the persistently high rates of adverse outcomes, including rehospitalization, in older HF patients.(4;16;28;29;37;38;41;42;45-47)

The typical older ADHF patient has > 5 comorbidities(14;48;49) and these contribute to impaired physical function(50) and subsequent adverse outcomes.(4;14;28;47;49;51-56) Impaired physical function and frequent non-cardiac comorbidities may explain the unexpected finding from multiple studies that > 50% of rehospitalizations in older ADHF patients are due to non-cardiac events rather than recurrent ADHF.(4;14;40;48;49;57-59)

In our published model,(14) we have identified 5 factors that contribute to severely impaired physical function and subsequent events in older ADHF patients: aging-related changes, the primary HF disease, deconditioning, multiple comorbidities, and iatrogenesis. Our data and others' from studies in other medical conditions common in older patients support that targeted physical function interventions can improve impairments related to each of these factors.(21;60-67)

However, current ADHF management paradigms do not account for or address the marked physical dysfunction in hospitalized older patients with acute HF.(3;4;50) This may also explain why trials of a wide range of interventions in ADHF have been largely negative(6-8;11;12;12) and disease management programs have had, at most, modest impact on long-term outcomes and mortality.(6;37;68;69)

Furthermore, the exercise training trials in HF to date (n >17) have systematically excluded ADHF patients in this key period of vulnerability.(70-73) The largest of these, the NIH-funded HF-ACTION trial, systematically excluded patients with ADHF and those within 6 weeks of hospital discharge.(73;74) Possibly because of recent instability, the study did not significantly reduce the primary endpoint of all-cause mortality or all-cause hospitalizations.(74) HF-ACTION also enrolled relatively few older patients, excluded those with multiple comorbidities, and utilized a traditional cardiac rehabilitation exercise training intervention that would not have been appropriate for older patients with significant frailty. As a result, and similar to prior trials, it likely missed the patients who are elderly, frail, and have multimorbidity who have the largest potential for improvements in outcomes.(3;3;4;75-77)

Prior exercise training studies in HF have not addressed the domains of balance and strength which are important for preventing early injuries in frail, older hospitalized ADHF patients (78) and for enhancing gains in function.(79) Prior intervention studies in older hospitalized patients that have included these domains have generally excluded patients with HF. (65;67;78-80) However, the results of such studies informed and support the primary hypothesis of the proposed study.(41;79-82) For instance, Morris et al showed that an early mobility program improved outcomes in older hospitalized patients with acute respiratory failure.(82) In a non-randomized quasiexperimental study, Tinetti et al. recently showed that a restorative home care model that included physical function reduced rehospitalizations by one-third in older patients, some of whom had HF.(41) The primary hypothesis is also supported by our pilot study which showed that in older patients with ADHF, the proposed intervention can improve SPPB score, a strong predictor of hospitalization, disability, and death.(38)

4. Overview of Investigational Plan

The REHAB-HF study is a multicenter, randomized, attention-controlled, single-blind trial of a novel, progressive, multi-domain rehabilitation intervention versus attention control in 360 older patients hospitalized with ADHF. The primary hypothesis is that the REHAB-HF intervention will improve physical function, as measured by the SPPB, the primary outcome.

Patients will be screened and enrolled during the index HF hospitalization. After completion of the baseline testing, participants will be randomly assigned to a novel, progressive, multi-

domain, 12-week physical function intervention or to attention control. Participants randomized to the intervention arm will begin a tailored, novel, multi-domain rehabilitation intervention in the hospital which will progress to the outpatient setting. The intervention will focus on four key physical functional domains: endurance, mobility, strength, and balance; and will be tailored based on participant performance in each of these domains. Participants randomized to the attention control arm will receive all services ordered by their primary physician and will be contacted bi-weekly by study staff. Blinded assessments will be repeated 1 month and 3 months following the index hospital discharge. Data on clinical events and resource use will be collected for 6 months following the index hospital discharge.

5. Study Population

The inclusion and exclusion criteria have been developed to include a broad range of older patients who are hospitalized with ADHF and expected to be discharged to home. To enhance the applicability of the results, the criteria are designed to be inclusive of older patients with multiple comorbidities, heterogeneous functional performance, and both preserved (≥ 45%) and reduced ejection fraction. Specifically, the study has the goal that patients with preserved ejection fraction will compromise at least 30% of the total study population.

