7.2 Rehabilitation Intervention Group

7.2.1 REHAB-HF Rehabilitation Intervention Overview

The multi-domain rehabilitation intervention for this study is a novel integration of rehabilitation therapies developed specifically for older heart failure patients who have been hospitalized for ADHF; a population characterized by heterogeneity in mobility status, multiple co-morbid conditions, and high rates of frailty.(48;50;83-85) The goal of the intervention is to increase endurance, mobility, strength, and balance utilizing reproducible targeted exercises administered by a multi-disciplinary team with specific milestones for progression.

This is a transitional intervention which begins during the acute hospitalization and continues for 12 weeks after discharge in the outpatient setting. The intervention will be administered once daily in the hospital and 3 days per week in the outpatient setting. Each session will include 3 stages: 1) warm-up (seated core exercises, 2-3 minutes light walking if able, and stretching exercises), 2) rehabilitation/training, and 3) cool-down (stretching exercises). The rehabilitation/training portion of each session will include exercises tailored based on participant performance in each of 4 domains: endurance, mobility, strength, and balance.

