7.2.2 Initiation of the Rehabilitation Intervention

Participants randomized to the multi-domain rehabilitation intervention will begin the intervention in the hospital as soon as possible after randomization. Though not required for enrollment, when possible the intervention will begin in the hospital. Plans for the initiation / continuation of the intervention in the outpatient setting will be made prior to hospital discharge and will be scheduled to begin within the first week following discharge.

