9.1 Follow up schedule

All baseline measures (see Table 2) will be collected during the index hospitalization. Follow up visits will occur 4 weeks ± 3 days and 12 weeks ± 10 days (unless intervention is extended, see section 7.3) from the day of discharge from the index hospitalization. These visits will include a brief history and physical and collection of study measures (see Table 2). Historical information will include heart failure symptoms, NYHA class, current medications, the results of any intervening cardiac studies (echocardiogram, stress tests, etc.), and the occurrence of any clinical events. The focused physical examination will include evaluation of the lungs, heart, and periphery. During these visits, the participants will also complete health status and quality of life measures as well as follow-up measures of physical function as detailed in Table 2 below. To promote retention, all participants will receive in-person contact within the first 2 weeks following discharge, achieved through intervention sessions, home visit, usual care clinic visit, or a scheduled clinic visit. In addition to the follow up visits, participants will receive a scheduled phone call at the end of months 2, 4, 5, and 6 to evaluate clinical status and for follow-up on adherence to the maintenance phase. Additional telephone contact will be made with the attention control group participants (see section 7.1). Telephone contact will also be maintained with participants unable or unwilling to attend the clinic visits. In some instances, participants unable to attend these visits may receive a home visit to collect important end points.

Table 2: Collection of Outcome Measures

	Index Hospitalization (Baseline)	1 Month (Visit)	2 Months (phone call)	3 Months (Visit)	4, 5, & 6 Months (phone call)
6MWT	X	X		X	
SPPB	X	X		X	
Grip	X	Х		Х	
Biomarkers	X			X	
Bioenergetic Profiling	Х			Х	

KCCQ	X	Х		Х	
SF-12	Х	Х		Х	
EQ-5D-5L	Х	X		X	X (6M only)
GDS-15	Х			Х	
LOT	Х			Х	
MoCA	Х			Х	
Clinical	Х	Х	Х	Х	Х
Events	^	^	^	^	^
Medications	Х	Х	Х	Х	Х
Review	Λ	^		X	^
Medical					
Resource		X	X	X	X
Use					

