11.4 Short-term Cost Analysis

We will compare mean direct medical costs, indirect (patient time) costs, total costs and quality-adjusted survival over the six-month follow-up period in the REHAB-HF intervention patients versus attention control. We will generate utility weights from the EQ-5D-5L collected data.

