12.3 Exploratory Efficacy Parameters

The study will explore several other possible endpoints:

- 1. Change in the Kansas City Cardiomyopathy Questionnaire (KCCQ) total score and physical component score at 3 months
- 2. Change in 6-minute walk distance (6MWD) at 3 months
- 3. Change in component scores of the SPPB at 3 months
- 4. Change in the 12-item short form health survey (SF-12), depression, and cognition measures at 3 months
- 5. Change in frailty status at 3 months
- 6. All-cause rehospitalizations at 1 month and 3 months
- 7. All-cause rehospitalizations 6 months from the date of randomization
- 8. All-cause combined rehospitalization and death at 6 months
- 9. Global rank endpoint of SPPB score + all-cause rehospitalization + death
- 10. Heart failure (HF)-specific rehospitalizations
- 11. Cardiovascular events
- 12. All-cause rehospitalization days
- 13. Total hospitalization days post-randomization
- 14. Total facility-free days alive
- 15. Deaths
- 16. Falls
- 17. Change in biomarkers at 3 months

13. Safety Monitoring and Adverse Events

Safety Monitoring and Adverse Events, including falls, will be collected at all visits, recorded with clinical details on the case report form, discussed during the regular Operations Committee meetings (Section 16), and forwarded to institutional review boards and the data safety monitoring board (DSMB; see section 12.2). An independent DSMB, appointed by NIH and governed by NIH policy, will meet semi-annually (or more frequently as indicated) and will monitor study-wide safety and clinical events.

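### The cost comparison has no randomization-based window: resource use is anchored at index discharge, and bed days between randomization and discharge have no stated place

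*Combined protocol and SAP*

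**What the plan says.** On the start of resource-use collection, Section 4 states: "Data on clinical events and resource use will be collected for 6 months following the index hospital discharge". In Section 9.1, under "Table 2: Collection of Outcome Measures", the medical resource use row is blank in the index-hospitalization column and marked at months 1, 2, 3 and 4 to 6.

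Section 11.4 will compare direct medical costs, patient-time costs, "total costs and quality-adjusted survival over the six-month follow-up period in the REHAB-HF intervention patients versus attention control". It does not say whether that period starts at randomization or at discharge. Section 11.1 lists hospitalizations among the items to be costed and has intervention resources documented for the whole study. It gives neither a start date.

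Treatment can start earlier than discharge. Section 1 says: "It will begin upon randomization during the hospitalization and will continue 3 times per week in an outpatient setting". Section 7.2.1 adds: "The intervention will be administered once daily in the hospital and 3 days per week in the outpatient setting". Section 7.2.2 qualifies this: "Though not required for enrollment, when possible the intervention will begin in the hospital".

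Other parts of the plan count from randomization. Section 10.6 collects clinical events from randomization until 6 months after discharge. In Section 12.3, exploratory endpoint 7 counts rehospitalizations over 6 months from randomization, and endpoint 13 is "Total hospitalization days post-randomization". Section 14.1 uses the duration of the index stay as a covariate in a supplemental rehospitalization analysis.

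**The concern.** The first of the other objectives in Section 2.3 is a comparison of medical costs between randomized arms. Such a comparison is protected by randomization only if both arms are followed from randomization, or from a time that treatment cannot move. Discharge is not such a time. Daily sessions may precede it, and Section 9.2 blinds only the outcome assessors, so the treating team may know the assignment when deciding on discharge.

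If the intervention shortens or lengthens the rest of the index stay, a window that opens at discharge misses that saving or cost. The direction cannot be told in advance. Section 11.6 relies on the net cost to judge whether the programme pays for itself and to propose payment models, so a missed component could carry into those conclusions. At the least, two analysts working from the same text could choose different windows and report different net costs.

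**Working it through.** The plan gives no figure for this window, so there is none to reproduce. The check sets the sections side by side and then illustrates the possible size.

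**1. What each section implies about the start of the clock**

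| Section | Subject | Start |
|---|---|---|
| 4 | Clinical events and resource use | Index discharge |
| 9.1, Table 2 | Resource use | No entry at the index stay; first entry at month 1 |
| 11.1 | Medical and intervention resources | Not stated |
| 11.4 | Costs and quality-adjusted survival | Not stated |
| 10.6 | Clinical events | Randomization |
| 12.3, item 7 | Rehospitalizations | Randomization |
| 12.3, item 13 | Hospital days | Randomization |

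For clinical events, Section 10.6 replaces the discharge start of Section 4 with a randomization start. No section does the same for resource use, so Section 4 remains the only stated rule.

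**2. Whether a randomization-based window is feasible**

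Randomization takes place in hospital, so it comes no later than discharge. Six months from randomization therefore ends no later than six months from discharge, and the planned follow-up covers it. Endpoint 13 already needs the bed days from randomization to discharge. The EQ-5D-5L is scheduled at baseline and at 1, 3 and 6 months, so utility is measured both before discharge and up to the end of follow-up.

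**3. Possible size (illustration only)**

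Inputs:
- d = 0.41 fewer rehospitalizations per participant, the design effect in Section 14.2.
- L = mean days per rehospitalization. Not in the documents; assumed 3, 5 or 7.
- x = between-arm difference in remaining index-stay days. Not in the documents; assumed 0.25, 0.5 or 1.

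Avoided rehospitalization days per participant = d × L: 0.41 × 3 = 1.23; 0.41 × 5 = 2.05; 0.41 × 7 = 2.87.

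Index-stay difference as a share of those days = x / (d × L):

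| x (days) | L = 3 | L = 5 | L = 7 |
|---|---|---|---|
| 0 | 0% | 0% | 0% |
| 0.25 | 0.25/1.23 = 20% | 0.25/2.05 = 12% | 0.25/2.87 = 9% |
| 0.5 | 0.5/1.23 = 41% | 0.5/2.05 = 24% | 0.5/2.87 = 17% |
| 1 | 1/1.23 = 81% | 1/2.05 = 49% | 1/2.87 = 35% |

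The table shows only that a modest index-stay effect, if there were one, would not be trivial beside the saving the trial is designed to detect. It is no evidence that such an effect exists.

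**The case against.** The strongest reply is that no section removes the index stay from the costs. Section 11.1 costs hospitalizations without a start date, Section 11.4 names none, and Section 4 is an overview whose window is already superseded for clinical events. The blank cell in Table 2 is also weak evidence: its column is the baseline assessment, which Section 6.3 places before randomization, so the blank does not show how far back the month 1 collection looks. These points stand. It would go too far to say that the plan definitely omits the remaining index stay. What remains is that the only stated resource-use window starts at discharge and nothing in Section 11 corrects it.

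A reader might also infer that the intervention arm is charged for inpatient sessions with no matching account of inpatient bed days. The documents do not support this. Section 11.1 names intervention resources and hospitalizations in the same sentence with no window for either, so the imbalance appears only if each is given a different one. Nor are deaths before discharge lost to the trial, since Section 10.6 collects events from randomization.

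Finally, a material effect on the index stay may be unlikely. Section 5.1 requires clinical stability at entry, Section 7.2.5 keeps inpatient intensity low, an inpatient start is not mandatory, and Section 7.2.12 yields to physician-ordered care. This is fair. It bears on the likely size of the bias and does not settle which window the analysis uses.

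**Conclusion.** The point holds as a defect in how the cost window is defined. As written, resource use is anchored at discharge in Section 4, the comparison in Section 11.4 has no anchor, and neither matches the randomization-based counting in Sections 10.6 and 12.3. Bed days between randomization and discharge have no stated place in the cost comparison.

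The size is unknown. Any bias depends on whether the intervention changes the remaining index stay; without such a change it is near zero, and with one it could go in either direction. The shares in the table rest wholly on assumed stay lengths and assumed differences. The consequence is limited to the economic objective and the sustainability assessment that uses it. The SPPB analysis and the 6-month rehospitalization analysis are not affected. The change is worth making because it is inexpensive and should be settled before cost data are seen by arm.

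**What to change.** In Sections 4, 11.1 and 11.4:

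- Define the window for costs and quality-adjusted survival as a fixed 6 months from randomization in both arms. A window running from randomization to 6 months after discharge would not be enough, because its end would still move with discharge.
- Include bed days from randomization to discharge in both arms, using the days already needed for exploratory endpoint 13.
- Apply the same window to the cost of inpatient intervention sessions.
- State how the part of the index admission after randomization is costed, for example per day. The hospital cost model in Section 11.1 uses length of stay, reason for admission and major procedures, and this admission began before randomization.
- Report the discharge-anchored result as a sensitivity analysis.

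The cost is mostly wording. Follow-up is not extended and the bed days are already needed. The downsides are some added variance from index-stay days, a costing rule for a partial admission, and possibly a Table 2 entry for procedures between randomization and discharge.
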